3. ENDPOINTS AND BASELINE VARIABLES: DEFINITIONS AND CONVENTIONS

3.1. Primary Endpoint(s)

Primary endpoints are:

- Incidence of treatment emergent AEs and SAEs, clinically significant changes in vital signs, ECG, and laboratory tests during the entire study;
- Incidence and severity of local skin irritation at times indicated in SoA.

3.2. Secondary Endpoint(s)

Secondary endpoints are:

- PF-07038124 PK parameters following topical application on Days 1 and 10, as data permit: AUC_{tau} , and C_{max} , if applicable.

CCI

3.4. Baseline Variables

There are no baseline variables used as covariates or stratification factors in this study.

The demographic and baseline characteristics data will include age, sex, ethnicity, race, weight, height, body mass index. Baseline variables are those collected on Day 1 prior to dosing or last measurement during screening visits before Day 1.

3.5. Safety Endpoints

3.5.1. Adverse Events

An adverse event is considered treatment emergent relative to a given treatment if:

- All events that start on or after the first dosing day and time/start time, if collected, but before the last dose plus the lag time.

The effective duration of treatment is determined by the lag time. The CDISC and Pfizer Standard (CaPS) default treatment LAG of 365 days post last dose of study drug will be used for this study.

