#### Schedule of Activities

Visit Identifier a Abbreviations used in this table may be found in Appendix 8 .	Screening		Treatment Phase											Follow-Up b	Early Termination/ Discontinuation
Days Relative to Day 1	-28 to -2	-1	1	2	3	4	5	6	7	8	9	10	11	38+3	
Informed consent	X														
CRU confinement c		X	→	→	→	→	→	→	→	→	→	→	→		
Outpatient visit	X														
Inclusion/exclusion criteria	X	X	X												
Randomization			X												
Medical/medication history (update)	X	X													
Physical exam d	X	X													X
Height and weight	X														
Review prior or concomitant treatments, as applicable	X	→	→	→	→	→	→	→	→	→	→	→	→	X	X
Safety laboratory, including fibrinogen and hsCRP e	X	X				X						X	X		X
Demography	X														
Contraception check	X	X												X	X
Single, supine 12-Lead ECG f	X		X		X							X	X		X
Single, supine BP and pulse rate, and temperature f	X		X		X							X	X		X
FSH g	X														
Pregnancy test (WOCBP only)	X	X										X			X
HIV, HBsAg, HBcAb, HCVAb, syphilis	X														
COVID-19 testing	X h					X									

PFIZER CONFIDENTIAL

Visit Identifier a Abbreviations used in this table may be found in Appendix 8 .	Screening		Treatment Phase											Follow-Up b	Early Termination/ Discontinuation	
			-28 to -2	-1	1	2	3	4	5	6	7	8	9	10	11	
Urine drug test	X	X														
Study intervention administration (QD) i			X	X	X	X	X	X	X	X	X	X	X	X		
Skin Irritation Evaluation j			X	X	X	X	X	X	X	X	X	X	X	X	X	
CCI																
CRU discharge l															X	
Serious and nonserious AE monitoring m	X	→	→	→	→	→	→	→	→	→	→	→	→	→	X	X
PK blood sampling n			X	X		X			X			X	X			X

- Day relative to start of study intervention (Day 1).
- All cohorts: Follow-up contact to occur 28-31 days post last dose with a phone call; additional follow-up at investigator discretion, including to monitor open AE, or based on emerging data.
- Participants will be admitted at least 12 hours prior to dosing. Admission procedures will be conducted once, unless deemed necessary by investigator or sponsor.
- Physical examination may be performed at non-specified timings if there are findings during the previous exam or new/open AEs, if appropriate and at investigator discretion.

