#### **8.3.1. Time Period and Frequency for Collecting AE and SAE Information**

The time period for actively eliciting and collecting AEs and SAEs (“active collection period”) for each participant begins from the time the participant provides informed consent, which is obtained before the participant’s participation in the study (ie, before undergoing any study-related procedure and/or receiving study intervention), through and including a minimum of 28 calendar days after the last administration of the study intervention.

Follow-up by the investigator continues throughout and after the active collection period and until the AE or SAE or its sequelae resolve or stabilize at a level acceptable to the investigator and Pfizer concurs with that assessment.

For participants who are screen failures, the active collection period ends when screen failure status is determined.

If the participant withdraws from the study and also withdraws consent for the collection of future information, the active collection period ends when consent is withdrawn.

If a participant definitively discontinues or temporarily discontinues study intervention because of an AE or SAE, the AE or SAE must be recorded on the CRF and the SAE reported using the CT SAE Report Form.

Investigators are not obligated to actively seek AE or SAE after the participant has concluded study participation. However, if the investigator learns of any SAE, including a death, at any time after a participant has completed the study, and he/she considers the event to be reasonably related to the study intervention, the investigator must promptly report the SAE to Pfizer using the CT SAE Report Form.

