#### Follow-up of AEs and SAEs

- The investigator is obligated to perform or arrange for the conduct of supplemental measurements and/or evaluations as medically indicated or as requested by the sponsor to elucidate the nature and/or causality of the AE or SAE as fully as possible. This may include additional laboratory tests or investigations, histopathological examinations, or consultation with other healthcare providers.
- If a participant dies during participation in the study or during a recognized follow-up period, the investigator will provide Pfizer Safety with a copy of any postmortem findings including histopathology.
- New or updated information will be recorded in the originally completed CRF.
- The investigator will submit any updated SAE data to the sponsor within 24 hours of receipt of the information.

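### SAP 3.5.1 defines treatment emergence by AE start time alone, so an acute AE already open before the first application that worsens on treatment is left out of the primary incidence tables

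*SAP*

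**What the plan says.** SAP 3.5.1 gives the only definition of treatment emergence in either document: "All events that start on or after the first dosing day and time/start time, if collected". The window closes a fixed lag after the final application, and the lag is set by the sentence that the "default treatment LAG of 365 days post last dose of study drug will be used for this study". Severity plays no part in the rule.

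Protocol 8.3.1 says that active AE collection "begins from the time the participant provides informed consent" and runs "through and including a minimum of 28 calendar days after the last administration of the study intervention". The Schedule of Activities shows AE monitoring from the screening visit, which can be up to 28 days before dosing.

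For an AE already reported, Protocol 10.3.3 (Follow-up of AEs and SAEs) says: "New or updated information will be recorded in the originally completed CRF". Neither document says that a rise in severity opens a new record or gives the event a new start date.

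Protocol 10.3.1 treats a flare of a chronic or intermittent condition that was already present as an AE. It does the same for clinically significant test results, including worsening from baseline, and for conditions first detected after dosing. SAP 6.1.1 leaves the listing and summarizing of AEs to sponsor reporting standards, which are not part of the documents.

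**The concern.** The incidence of treatment-emergent AEs is the first primary endpoint (SAP 3.1). A drug can harm by making an existing symptom worse as well as by causing a new one, and a rule that looks only at start time counts only the second kind.

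The symptoms for which this could matter are relevant to this compound. Headache, dizziness and nausea were reported in the first study (Protocol 2.2.4.1). Nervous-system and gastrointestinal effects are listed as class risks (Protocol 2.3.1). Such symptoms can be mild before dosing and stronger afterwards.

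The study tests no hypothesis, so the descriptive counts are the result. With 4 active and 2 vehicle participants per cohort, one classification can change a reported percentage visibly.

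**Working it through.** **Timeline.** Inputs: screening up to 28 days, treatment 10 days, follow-up 28 days (Protocol 4.1). 28 + 10 + 28 = 66 days, which reproduces the stated participation time of about 66 days. AEs can therefore be on record for up to 28 days before the first application.

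**Applying the rule to an example.** Take an acute AE, not a flare of a known condition, that starts as mild on Day -1 and becomes severe on Day 5.

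1. Is it collected? Yes. Onset is after consent (Protocol 8.3.1).
2. Where does the worsening go? Into the record already completed (Protocol 10.3.3). On that reading the start stays at Day -1.
3. Does the exacerbation clause in Protocol 10.3.1 create a new AE? Not on its wording, because the event is neither a chronic nor an intermittent condition that predated the study.
4. Is it treatment-emergent under SAP 3.5.1? The start must be on or after Day 1 dosing. Day -1 is earlier, so no.

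The event appears in the AE listing but not in the treatment-emergent incidence table.

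**Size of one such case.** Change in incidence = 1/n, for a participant with no other treatment-emergent AE:

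| Group | n | Shift (percentage points) |
|---|---|---|
| Active, one cohort | 4 | 1/4 = 25 |
| Vehicle, one cohort | 2 | 1/2 = 50 |
| Vehicle, pooled (SAP 6) | 2 + 2 = 4 | 1/4 = 25 |

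If the participant already has another treatment-emergent AE, overall incidence does not move. Only the row for that event and the severity breakdown would change.

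**How often.** The documents give no rate. As an assumption only, let p be the chance that a participant has an acute pre-dose AE that worsens on treatment. The expected number of such participants is 12p, and the chance of none is (1 - p)^12:

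| Assumed p | Expected number | Chance of none |
|---|---|---|
| 0.01 | 0.12 | 0.89 |
| 0.05 | 0.60 | 0.54 |
| 0.10 | 1.20 | 0.28 |

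The eligibility criteria argue for the low end.

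**The case against.** **Existing provisions may cover the gap.** Protocol 10.3.1 gives flares of chronic or intermittent conditions, and clinically significant test results that worsen, a route to an on-treatment start. That stands, so a reader who infers that every pre-dose problem that worsens is lost would go too far. The route does not reach an acute AE that is already open.

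**The retained start date is inferred.** Protocol 10.3.3 says where new information goes, not what happens to the start date, and the sponsor standards might open a second record. This is fair as a caution. But SAP 6.1.1 defers only listing and summarizing to those standards. The definition itself is written out in SAP 3.5.1, and a programmer following it would exclude the event.

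**Such events are unlikely.** Participants must be overtly healthy, acute unstable illness within 7 days of Day 1 is exclusionary, and eligibility is rechecked on Day -1 and Day 1. This makes the case rare, not impossible: a mild symptom need not breach any of these criteria.

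**Nothing is hidden.** All AEs are listed, and safety data are reviewed during the study (Protocol 9.4.6). Skin scores, vital signs, ECG and laboratory values have their own summaries, which do not depend on treatment-emergent status. That stands and limits the harm to the incidence table.

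**The 365-day lag.** A reader might infer that it leaves the window open-ended, or unequal between participants. The documents do not support that. The lag is a fixed cap, the same for everyone relative to last dose, and the "Follow-up contact to occur 28-31 days post last dose with a phone call" is timed the same way. The cap falls on Day 10 + 365 = Day 375, and the scheduled contact on Day 38 to 41, so the lag is much longer than scheduled collection. The protocol does allow "additional follow-up at investigator discretion, including to monitor open AE, or based on emerging data", so an occasional late event could come from a participant who was followed longer. In practice, though, the lag counts every post-dose AE that is recorded, which fits an endpoint defined over the whole study. Ending the window at the call would be a debatable choice and less conservative for safety.

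**Conclusion.** The point holds for one class of event: an acute AE that is open before the first application and increases in severity on treatment. As written, SAP 3.5.1 keeps it out of the primary incidence tables, although it would still be listed.

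The expected effect is small, possibly no events among 12 participants. If one occurs, the shift is 25 or 50 points depending on the group.

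This rests on two assumptions: that a severity update leaves the recorded start unchanged, and that no unseen sponsor standard overrides the definition in the SAP. The percentage-point figures also assume that the participant has no other treatment-emergent AE. The difference between the lag and the scheduled collection period has little practical effect and is not part of the conclusion.

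**What to change.** Add to the definition in SAP 3.5.1: *or starts before the first application and increases in severity on or after it*. State that the comparison is with the last severity before the first application, using the mild, moderate and severe categories in Protocol 10.3.3.

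Add a CRF completion instruction so that the worsening and its date are captured on the AE page, for example as a new AE record. If sponsor standards already do this, cite them in SAP 3.5.1.

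The cost is one SAP clause with its reference point and one CRF instruction, settled before unblinding. Design, sample size, participant procedures and the 365-day lag stay as they are.

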3.5.2. Laboratory Data

Safety laboratory tests will be performed as described in the protocol.

To determine if there are any clinically significant laboratory abnormalities, the hematological, clinical chemistry (serum) and urinalysis safety tests will be assessed against the criteria specified in the sponsor reporting standards. The assessment will not take into account whether each participant's baseline test result is within or outside the laboratory reference range for the particular laboratory parameter.

Baseline will be the last predose measurement.

3.5.3. Vital Signs

Supine blood pressure and pulse measurements will be taken at all time points listed in the Schedule of Activities given in the protocol.

Baseline will be defined as the last predose recording.

The following vital signs endpoints will be determined:

- The maximum decrease and increase from baseline over all measurements taken postdose for supine systolic and diastolic blood pressures;
- The maximum decrease and increase from baseline over all measurements taken postdose for supine pulse rate.

The maximum increase from baseline will be calculated by first subtracting the baseline value from each postdose measurement to give the change from baseline. The maximum of these values over the treatment period will then be selected, except in the case where a participant does not show an increase. In such an instance, the minimum decrease should be taken.

Similarly, the maximum decrease from baseline will be determined by selecting the minimum value of the change from baseline. In cases where a participant does not show a decrease, the minimum increase should be taken.

3.5.4. Electrocardiograms

Standard 12-lead ECGs will be taken at all time points listed in the Schedule of Activities given in the protocol.

Baseline will be defined as the single supine 12-lead ECGs predose recording.

The QT, QTcF, PR, QRS and heart rate will be recorded at each assessment time.

If not supplied, QTcF will be derived using Fridericia's heart rate correction formula:

$$QTcF = QT / (RR)^{1/3} \quad \text{where } RR = 60/HR \text{ (if not provided)}$$

The maximum absolute value (postdose) and the maximum increase from baseline will be determined over all measurements taken postdose for QTcF, QT, heart rate, PR and QRS.

The maximum increase from baseline will be calculated by first subtracting the baseline value from each postdose measurement to give the change from baseline. The maximum of these values over the treatment period will then be selected, except in the case where a participant does not show an increase. In such an instance, the minimum decrease should be taken.

3.5.5. Skin Irritation Assessment

Local toleration will be assessed by Draize scoring and clinical observation in Table 2.

All numerical, letter grades, and superficial observations will be collected on the designated CRF.

Table 2. Skin Irritation Assessment Using Draize Scoring

Definition	Score
No reaction visible	0
Trace reaction – barely perceptible pinkness	1
Mild reaction – readily visible pinkness	2
Moderate reaction – definite redness	3
Strong to severe reaction – very intense redness	4

Definition of letter grades appended to a numerical grade:

J	Burning, stinging, itching
E	Edema – swelling, spongy feeling when palpated
P	Papules – red, solid, pinpoint elevations, granular feeling
V	Vesicles – small elevation containing serous fluid (blister-like), diameter 5 mm or less
B	Bulla reaction – fluid-filled lesion greater than 0.5 cm in diameter
S	Spreading – evidence of the reaction beyond the test site
W	Weeping – result of a vesicular or bulla reaction – serous exudates – clear fluid oozing or covering test area
I	Induration – solid, elevated, hardened, thickening skin reaction
XC	Additional comments appear in Comments section

Definition of superficial observations appended to a numerical and/or letter grade:

G	Glazing
Y	Peeling
C	Scab, dried film of serous exudates of vesicular or bulla reaction
D	Hyperpigmentation (reddish-brown discolored of test area)
H	Hypopigmentation (loss of visible pigmentation at test area)
F	Fissuring – grooves in the superficial layers of the skin to glistening
R	Erosion(s)
U	Ulceration(s)
K	Scaling – flaking of skin

3.5.6. Other Safety Data

Additional safety data, body temperature, fibrinogen and hsCRP will be collected as described in the protocol and will be listed (if collected in the sponsor's database).

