#### **9.4.6. Other Safety Analyses**

AEs, ECGs, BP, pulse rate, temperature, and safety laboratory data will be reviewed and summarized on an ongoing basis during the study to evaluate the safety of participants. Any clinical laboratory, ECG, BP, and pulse rate abnormalities of potential clinical concern will be described. Safety data will be presented in tabular and/or graphical format and summarized descriptively, where appropriate.

Medical history and physical examination and neurological examination information, as applicable, collected during the course of the study will be considered source data and will not be required to be reported, unless otherwise noted. However, any untoward findings identified on physical and/or neurological examinations conducted during the active collection period will be captured as AEs, if those findings meet the definition of an AE. Data collected at screening that are used for inclusion/exclusion criteria, such as laboratory data, ECGs, and vital signs, will be considered source data, and will not be required to be reported, unless otherwise noted. Demographic data collected at screening will be reported.

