6.1. Primary Endpoint(s)

The primary endpoints of this study are the standard safety endpoints and local skin irritation presented in the Section 3.1. A set of summary tables split by cohort and treatment group (including pooled vehicle group) will be produced to evaluate potential risk associated with the safety and toleration of administering PF-07038124.

No formal analyses are planned safety data. The safety endpoints will be listed and summarized in accordance with the sponsor reporting standards, where the resulting data presentations will consist of participants from the safety analysis set.

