6.1.2. Laboratory Data

Laboratory data will be listed and summarized in accordance with the sponsor reporting standards. Baseline is as defined in Section 3.5.2.

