6.1.3. Vital Signs Data

Absolute values and changes from baseline in supine systolic and diastolic blood pressure and pulse rate will be summarized by cohort, treatment group and postdose timepoints, according to the sponsor reporting standards. Tables will be paged by parameter. Baseline is as defined in Section 3.5.3.

Mean changes from baseline for systolic and diastolic blood pressure and pulse rate will be plotted against time postdose. On each plot there will be 1 line for each treatment. Data from all cohorts will be plotted on the same figure using separate lines for the 2 vehicles. Corresponding individual plots of change from baseline will also be produced for each cohort and treatment.

Maximum absolute values and changes from baseline for vital signs will also be summarized descriptively by treatment and cohort using categories as defined in [Appendix 1](#). Numbers and percentages of participants meeting categorical criteria will be provided. All planned and unplanned postdose timepoints will be counted in these categorical summaries. All values meeting the criteria of potential clinical concern will be listed.

If necessary, maximum increases or decreases in vital signs may be summarized in addition to the above.

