6.6. Safety Summaries and Analyses

The details of safety analyses are described in the Section [6.1](#).

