Appendix 1. Categorical Classes for ECG and Vital Signs of Potential Clinical Concern

CATEGORIES FOR QTcF

QTcF (ms)	450≤ max. <480	480≤ max.<500	max. ≥500
QTcF (ms) increase from baseline	30≤ max. <60	max. ≥60	

CATEGORIES FOR QT

QT (ms)	max. ≥500		
---------	-----------	--	--

CATEGORIES FOR PR AND QRS

PR (ms)	max. ≥300	
PR (ms) increase from baseline	Baseline >200 and max. ≥25% increase	Baseline ≤200 and max. ≥50% increase
QRS (ms)	max. ≥140	
QRS (ms) increase from baseline	≥50% increase	

CATEGORIES FOR VITAL SIGNS

Systolic BP (mm Hg)	min. <90	
Systolic BP (mm Hg) change from baseline	max. decrease ≥30	max. increase ≥30
Diastolic BP (mm Hg)	min. <50	
Diastolic BP (mm Hg) change from baseline	max. decrease ≥20	max. increase ≥20
Supine pulse rate (bpm)	min. <40	max. >120
Standing pulse rate (bpm)	min. <40	max. >140

Measurements that fulfill these criteria are to be listed in report.

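### The laboratory abnormality count ignores baseline although the primary endpoint is change, and SAP 3.5.6 names only a listing for fibrinogen and hsCRP although SAP 6.1 and 6.1.2 call for summaries

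*SAP*

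**What the plan says.** **Laboratory abnormalities.** SAP 3.1, like protocol section 3, defines the laboratory part of the primary endpoint as clinically significant changes over the whole study. SAP 3.5.2 assesses hematology, serum chemistry and urinalysis results against the sponsor's criteria and states that the participant's baseline status relative to the reference range plays no part in that assessment. The same section defines baseline as the last measurement before dosing.

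**Fibrinogen and hsCRP.** SAP 3.5.6 says that "body temperature, fibrinogen and hsCRP will be collected as described in the protocol and will be listed", on condition that they are in the sponsor's database. SAP 6.1 says "The safety endpoints will be listed and summarized in accordance with the sponsor reporting standards" and, for the primary safety objective, "A set of summary tables split by cohort and treatment group (including pooled vehicle group) will be produced". SAP 6.1.2 says "Laboratory data will be listed and summarized in accordance with the sponsor reporting standards".

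The protocol's Schedule of Activities includes both markers in the safety laboratory row. Section 4.2 adds them to the safety laboratory assessments because of toxicology findings. Section 2.3.1 names fibrinogen and C-reactive protein as acute-phase monitoring under the vasculitis risk.

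**The concern.** The endpoint asks what changed after dosing. The SAP 3.5.2 count answers a different question: who has a value that meets the criteria, whether or not it was already abnormal. With groups of 2 or 4, one participant with a long-standing abnormality can make an arm look affected.

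For fibrinogen and hsCRP, two competent programmers could produce different outputs from the same SAP: a listing only, following 3.5.6, or a listing and a summary, following 6.1 and 6.1.2. At stake is whether the report compares the markers chosen to watch a named risk with pooled vehicle in a prespecified table.

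**Working it through.** **Design figure.** Protocol 9.2 gives 4 active and 2 vehicle in each of two cohorts: 2 × (4 + 2) = 12, as stated. SAP section 6 pools vehicle across cohorts: 2 + 2 = 4. The five reporting groups are therefore active (n = 4) and vehicle (n = 2) in each cohort, plus pooled vehicle (n = 4).

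**Part 1: effect of ignoring baseline.** One participant whose value meets the criteria before dosing and is unchanged afterwards adds:
- 1/4 = 25 percentage points in an active arm or in pooled vehicle;
- 1/2 = 50 percentage points in the vehicle group of one cohort.

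Take an active arm of 4 with one participant counted as abnormal:
- *New abnormality, all four baselines normal:* the plan reports 1/4. Split by baseline, it reads 1/4 with normal baseline, and nobody has an abnormal baseline.
- *Unchanged abnormality, one baseline abnormal:* the plan also reports 1/4. Split by baseline, it reads 0/3 with normal baseline and 1/1 with abnormal baseline.

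The planned count is the same in both cases, and the split tells them apart. The split does not separate a persisting abnormality from one that worsened; the listing is needed for that.

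The eligibility rules make such participants less likely but do not exclude them. Exclusion 13 sets numeric limits only for AST, ALT and bilirubin. Other laboratory values are left to judgment, through inclusion 2, exclusion 5 and the requirement that screening results be acceptable.

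**Part 2: fibrinogen and hsCRP.**
- SAP 6.6 sends the reader to 6.1 for detail ("The details of safety analyses are described in the Section" 6.1). Subsections 6.1.1 to 6.1.5 correspond one to one with 3.5.1 to 3.5.5. Nothing in 6.1 corresponds to 3.5.6.
- SAP 6.1.2 covers laboratory data and makes no exception for the two markers. SAP 3.5.6 sets them apart as additional data.
- SAP 5.2.2 summarizes continuous endpoints unless otherwise specified, and 3.5.6 can be read as specifying otherwise. The default does not settle the matter.
- SAP 3.5.2 names hematology, chemistry and urinalysis, while protocol Table 6 puts the two markers in its Other column. It is therefore also unclear whether any abnormality criterion applies to them.

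Volume of data: the Schedule of Activities has safety laboratory samples on Day -1 and Days 4, 10 and 11.
- Post-baseline values: 3 days × 12 participants = 36 per marker, and 2 × 36 = 72 in all.
- A full summary including baseline: 5 groups × 4 days × 2 markers = 40 rows.

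**The case against.** The strongest reply is that nothing is lost. Listings of 12 participants show every value, including the predose one. Protocol 8.2.4 has the investigator record clinically relevant laboratory changes as adverse events, and these are summarized as part of the primary endpoint. Summaries of 2 or 4 values hold less information than the listing itself.

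The SAP 3.5.2 rule is stated openly and looks deliberate. Because 3.5.2 defines a baseline and 6.1.2 refers to it, the sponsor's reporting standards, which are not in the documents, may already produce change-from-baseline tables. For the two markers, 3.5.6 is a specific instruction that follows the Other column of protocol Table 6, so it can be read as a choice.

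Much of this stands. It limits the impact, and it means that 3.5.2 is a limitation of the count rather than a contradiction. It does not remove the point. Adverse event recording leaves the abnormality count as it is, and a listing gives no comparison with pooled vehicle. The documents also do not show what the sponsor standards contain.

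Three stronger readings may tempt a reader, and the documents do not support them:
- *A conflict with protocol 9.4.6.* The sentence "AEs, ECGs, BP, pulse rate, temperature, and safety laboratory data will be reviewed and summarized on an ongoing basis during the study" concerns review while the study runs. The section's general reporting sentence applies only where appropriate, and protocol section 9 lets the SAP modify the protocol.
- *Temperature as an omission.* SAP 6.1.3 reads "Absolute values and changes from baseline in supine systolic and diastolic blood pressure and pulse rate will be summarized by cohort, treatment group", and the Appendix 1 table headed "CATEGORIES FOR VITAL SIGNS" has no temperature row. But 3.5.6 assigns temperature an output, the listing, and the abnormalities that protocol 9.4.6 says will be described do not name temperature either.
- *A probability that an arm contains a participant with a persisting abnormality.* The documents give neither a rate nor the abnormality criteria, so any such figure would rest on an invented input.

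**Conclusion.** The point holds as a low-impact, descriptive improvement. The SAP 3.5.2 count cannot separate new from pre-existing abnormalities, although the endpoint is worded as change. Each unchanged pre-existing abnormality adds 25 percentage points in a group of 4. That figure is conditional on such a participant being present; how often that would happen cannot be estimated from the documents.

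For fibrinogen and hsCRP the inconsistency lies within the SAP, between 3.5.6 and 6.1 with 6.1.2. Section 3.5.6 names a listing and does not forbid a summary, so it would be too strong to say that the SAP rules one out. The case for the summary rests on the protocol's own classification of the markers as safety laboratory tests and on their stated role under the vasculitis risk. No hypothesis test or sample size is affected.

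**What to change.** 1. In SAP 3.5.2 and 6.1.2, keep the overall abnormality count and also present it by normal versus abnormal baseline, using the last predose measurement already defined in 3.5.2.
2. Reconcile SAP 3.5.6 with 6.1.2. In addition to the listing, summarize observed values and changes from baseline for fibrinogen and hsCRP by cohort, treatment (including pooled vehicle) and scheduled day (Days -1, 4, 10 and 11). State whether the abnormality criteria apply to them.
3. Optionally, add temperature to the vital-signs summary in 6.1.3 for consistency.

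If the sponsor standards already provide items 1 and 2, a sentence in the SAP saying so is enough.

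The cost is a few sentences, 40 descriptive rows for the two markers and a split of an existing count. The data are already scheduled. The drawback is small tables: the baseline split will have cells of 0 to 4, so they should be read alongside the listings.
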